¹⁵ AEs and SAEs will be collected starting from the time that the Informed Consent is signed. AEs and AEs of special interest (AESIs) will be collected at each study visit. During follow-up period beyond study completion or after an ET, only those SAEs considered to be related to study treatment should be reported.

¹⁶ Unscheduled or early termination (ET) visits may occur at any time. Unscheduled visits (UVs) may occur to assess AEs or disease progression, for example. It is left to Investigator discretion to determine what if any assessments are appropriate for an UV, however VS, physical examination, assessment of injection sites, query subject for any AEs and new concomitant medications or treatments at the minimum should be performed. UVs occurring after W24 may be scheduled to follow AEs to resolution or establishment of a new baseline (progression of AE has been stabilized) or for assessments regarding disease progression. After an ET, a visit should be scheduled promptly to determine the reason for ET and to perform study closeout assessments assuming the subject is willing to return to the clinic and undergo such procedures. Note that subjects who develop any CTCAE grade 2 or higher cardiovascular or respiratory TEAE or any grade 3 or higher TEAE involving other organ systems must be discontinued from further study treatment dosing and monitored until resolution or stabilization.

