7.1.2.3. AD Flares and Rescue Treatment

AD is a chronic relapsing skin condition that is characterized by periods of disease flare or escalation of symptoms. Many flare definitions rely on a physician's assessment or subject report (38), however a relatively recent review suggests that an escalation of treatment (or rescue) and days of topical corticosteroid (TCS) use were good indicators of flare and flare duration (39). Therefore, when an AD flare occurs, its onset and duration will be documented as an AE by the location(s) of flare involvement. If the Investigator determines that the flare is severe enough to merit "rescue" treatment, document the choice of TCS and

instructions for its use and the duration of such permitted rescue TCS treatment. The subject need not be discontinued in this situation. Permitted TCS medications to treat AD flares may include the following:

- Cream based preparations or lotion in hair bearing areas
- Low to moderate potency TCS (WHO classification VII-IV) equivalent to class VII – IV according to the U.S classification are allowed. The TCS regimen will be adjusted to the flare activity and tolerability by the subject, and stopped when lesions are cleared.
 - Examples:
 - Methylprednisolone acetate 0.1%
 - Mometasone furoate 0.1%
 - Betamethasone valerate cream 0.1%
- If possible, Investigators should attempt to limit the first step of rescue therapy to permitted TCS rescue treatment and escalate to systemic medications only for patients who do not respond adequately after the treatment of permitted TCS.

If a patient receives any other rescue treatment including other topical rescue treatments (apart from permitted TCS and bland emollients), systemic corticosteroids or nonsteroidal systemic immunosuppressive/immunomodulating drugs (cyclosporine, methotrexate, mycophenolate mofetil, azathioprine, Janus kinase inhibitors, biologic agents, etc), the study treatment will be immediately discontinued. In this situation, subjects should remain in the study and continue with study procedures (complete the schedule of study visits and assessments) but will not receive additional study drug administration.

Investigators should make every attempt to conduct efficacy and safety assessments (eg, disease severity scores, safety labs) immediately before administering any rescue treatment. An unscheduled visit may be used for this purpose if necessary.

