7.1.7. Early Termination (ET) Visit (+7d)

Subjects who prematurely discontinue from the study will be requested to come in at their convenience for assessments which are normally planned for the end of the study (see Schedule of Events ([Table 1](#)) for details of study procedures), if appropriate, and 2 post-treatment follow-up period visits within the 8 weeks following the last dose of study treatment. If subjects are not willing to return for a full complement of early termination assessments, request that they come in to at least assess for any TEAEs.

- Document reason for and date of decision to ET
- Document any new AEs
- Document clinically significant AD flares requiring TCS treatment
- Document any new or changed concomitant medications or treatments
- Subject itch diary review
- Perform prior injection site assessment
- Perform safety labs, PK, PD and ADA samples per Schedule of Events ([Table 1](#))
- Physical examination per Schedule of Events ([Table 1](#))
- Record VS. Note that subjects should be seated and rested for at least 3 minutes prior to assessing VS.
- Repeat Investigator AD assessments (IGA, EASI, BSA and SCORAD) and Subject PROs (review PP-NRS with subject, complete DLQI and POEM) per Schedule of Events ([Table 1](#))

For subjects who fail to return to the site, the Investigator should make the best effort to recontact the patient (eg, contacting patient's family or private physician, reviewing available registries or health care databases) and report their ongoing status. Attempts to contact such patients must be documented in the patient's records (eg, times and dates of attempted telephone contacts, and receipt for sending a registered letter). A subject should only be designated as lost to follow-up if the site is unable to establish contact with the subject after a minimum of 2 documented attempts (phone, text, e-mail, certified letter, etc.).

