11.1.4. General Guidelines for AE Reporting

Collection of AEs and SAEs will commence from the time the subject signs the informed consent to participate in the study and continue until the end of the study. All AEs must be entered on the corresponding pages of the CRF, regardless of causality or severity. AEs include new AEs, worsening baseline conditions, clinically significant laboratory findings, disease-related signs and symptoms that were not present at baseline, and any events or findings that the Investigator feels are clinically significant.

Information collected concerning AEs will include the following:

- Name of the event (whenever possible, diagnosis or single syndrome should be reported instead of symptoms)
- Start date
- Stop date
- Severity (i.e., mild, moderate, severe, potentially life-threatening, death)

- Relationship to study treatment (related, not related)
- Action taken with the study treatment (dose not changed, drug interrupted, drug withdrawn, not applicable, unknown)
- Outcome (recovered/resolved, recovering/resolving, not recovered/not resolved, resolved with sequelae, fatal, unknown)
- Seriousness of event (SAE or non-SAE)

Pretreatment AEs are defined as any untoward medical occurrence in a clinical investigation subject who has signed informed consent to participate in a study but prior to administration of any study medication; it does not necessarily have to have a causal relationship with study participation. Treatment-emergent adverse events (TEAEs) are defined as AEs that developed or worsened during the treatment-emergent period. The treatment-emergent period is from first administration of study treatment to end of the follow-up period. Pre-existing conditions (present at the time of signing of informed consent) are considered concurrent medical conditions and should not be recorded as AEs unless they worsen in severity or increase in frequency. Screening evaluation findings (e.g., laboratory tests, ECG, etc.) should not be recorded as Pretreatment AEs unless related to study procedures.

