The Investigator should take appropriate measures to follow all AEs until clinical recovery is complete and laboratory results have returned to normal, or until progression has been stabilized, or until death, in order to ensure the safety of the subjects. This may imply that observations will continue beyond the last planned visit per protocol, and that additional investigations may be requested by the monitoring team up to as noticed by the sponsor. Subjects who experience an ongoing SAE or an AESI, at the prespecified study end-date, should be followed until resolution, stabilization, or death and related data will be collected.

When treatment is prematurely discontinued, the subject's observations will continue until the end of the study as defined by the protocol for that subject.

Laboratory, vital signs or ECG abnormalities should be recorded as AEs when any of the following conditions are met:

- Test result is associated with accompanying symptoms; and/or
- Test result requires additional diagnostic testing or medical/surgical intervention; and/or
- Test result leads to a change in study dosing (outside of any protocol-specified dose adjustments) or discontinuation from the study, significant additional concomitant drug treatment, or other therapy; and/or
- Test result is considered to be an AE by the investigator or sponsor.

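### Table 1 footnote 15 limits reporting after an early termination to related SAEs, which contradicts Protocol Sections 7.1.7, 11.1.4 and 11.1.6 and should be reworded

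*Protocol*

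**What the plan says.** Footnote 15 to Protocol Table 1 starts AE and SAE collection at consent. It then says that "AEs and AEs of special interest (AESIs) will be collected at each study visit". Its last sentence adds that, in follow-up past study completion or once an ET has occurred, "only those SAEs considered to be related to study treatment should be reported".

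Other current text bears on the same period:

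- **Section 7.1.7** asks subjects who leave early for an ET visit and, if appropriate, "2 post-treatment follow-up period visits within the 8 weeks following the last dose of study treatment". A subject unwilling to complete all ET assessments is asked to attend at least for a check of treatment-emergent events.
- **Section 11.1.4** has AE and SAE collection start when the subject signs consent "to participate in the study and continue until the end of the study", with every AE entered whatever its cause or severity. It adds: "The treatment-emergent period is from first administration of study treatment to end of the follow-up period".
- **Section 11.1.5** requires immediate notification of AESIs, serious or not.
- **Section 11.1.6** limits SAE reporting to causally suspected events only once the study has ended for the subject. It does not mention ET.
- **SAP Section 9.B** counts as treatment-emergent any AE that begins or worsens after treatment starts, with no cut-off at ET.

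On stopping treatment without leaving the study, Section 11.1.4 says that observations "will continue until the end of the study as defined by the protocol for that subject". After a rescue treatment that ends dosing, Section 7.1.2.3 says that "subjects should remain in the study and continue with study procedures".

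**The concern.** The footnote is attached to the table that sites work from at each visit. Read as written, it tells a site not to report most of what the two post-ET visits could find: a non-serious conjunctivitis, any other non-serious AE, or a hospitalisation judged unrelated. The SAP's TEAE and AESI tables assume that such events are in the database and cannot recover them if they are not.

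What is recorded after ET would then depend on which passage a site follows and, for SAEs, on the investigator's causality call. Protocol Section 5.4.2 gives a median half-life of about 10 days, so the first weeks of this window still carry drug exposure. AD flares are also recorded as AEs (SAP Section 8.D), so a non-serious flare after ET but before Week 16 could drop out of the flare counts.

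**Working it through.** **Side by side.** Take an event that first appears at a post-ET visit within 8 weeks of the last dose.

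| Event | Footnote 15, last sentence | Rest of the documents |
|---|---|---|
| Non-serious AE | not reported | entered whatever the cause (11.1.4); TEAE (11.1.4, SAP 9.B) |
| Non-serious AESI | not reported | collected at each study visit (footnote 15, preceding sentence); immediate notification (11.1.5) |
| SAE judged unrelated | not reported | reported within 24 hours (11.1.6); TEAE |
| SAE judged related | reported | reported |

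Three of the four rows conflict. The half of the sentence about the time beyond study completion agrees with Section 11.1.6. Only the ET half is at fault.

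**Who is covered.** The synopsis (Study Periods) and Section 7.1.7 use ET for leaving the study. On that meaning, subjects who stop only treatment are outside the footnote (Sections 7.1.2.3 and 11.1.4). However, the synopsis row on mandatory early termination and Section 11.2 use the same term for stopping treatment. A site that took ET in that sense would cut reporting in subjects whom the protocol keeps under observation.

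**Size, as an upper bound.** Inputs: 220 randomised, 55 per arm, 20% dropout (Protocol Section 13.2); 8 weeks after last dose (Section 7.1.7).

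- The plan's own completer count reproduces: 55 × (1 − 0.20) = 44 per arm, so 11 dropouts per arm.
- Subjects, if every dropout is an ET: 4 × 11 = 44 of 220.
- Subject-weeks, if all 8 weeks are lost for each: 44 × 8 = 352.
- Planned post-treatment subject-weeks: 220 × 8 = 1,760. Share: 352 / 1,760 = 20%.
- Share of the whole 24-week period: 352 / (220 × 24) = 352 / 5,280 = 6.7%.
- If ETs ran from 5% to 30% (assumption): 11 to 66 subjects and 88 to 528 subject-weeks.

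The gap opens at the ET visit, not at the last dose, because Table 1 and Section 7.1.7 record AEs at that visit. If that visit fell one dosing interval (2 weeks) after the last dose (assumption), the bound would be 44 × 6 = 264 subject-weeks, or 264 / 1,760 = 15%. Subjects who refuse further visits lower it again.

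**Residual exposure.** With a 10-day half-life and simple exponential decline (assumption), the fraction remaining at day t is 0.5^(t/10): 38% at 14 days, 14% at 28 days, 2% at 56 days.

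Sample size, alpha and power are not affected.

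**The case against.** The best defence is that ET is the subject's end of study. Footnote 15, Section 11.1.6 and the collection period in Section 11.1.4 would then agree. A site could also treat the two post-ET contacts as study visits, collect all AEs there under the footnote's preceding sentence, and apply the related-SAE rule only once contact has ended. Section 11.1.4 also has ongoing SAEs and AESIs followed to resolution, so an AESI already open at ET is not dropped.

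Part of this stands: a careful site could reach a sensible practice. But reading ET as the end of study leaves the two visits in Section 7.1.7 without a reporting rule and cuts short a treatment-emergent period that runs to the end of follow-up. The visit-based reading is workable only by setting aside the words about ET.

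Three stronger inferences are tempting, and the documents do not support them:

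- *Safety data are truncated in everyone who stops.* Subjects who stop only treatment stay under full collection, and AEs up to and at the ET visit are recorded.
- *The arms are compared unfairly.* No difference in dropout between arms is shown, and no formal safety comparison is planned (Protocol Section 13.7, SAP Section 9). Unequal observation time also follows from dropout itself: a subject last dosed at Week 4 would be followed only to about Week 12 even with the footnote corrected.
- *The subjects affected are those most likely to have had a problem.* Safety is one listed reason for leaving (Section 8.3), but so are administrative reasons and loss to follow-up.

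**Conclusion.** The contradiction is real. For subjects who leave the study, footnote 15 states a reporting rule that four other statements in the protocol do not allow: its own preceding sentence and Sections 7.1.7, 11.1.4 and 11.1.6. This is a wrong stated rule, not a missing detail. Followed literally, it loses non-serious AEs, AESIs and unrelated SAEs between the ET visit and the end of the Section 7.1.7 follow-up.

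The reach is limited. The 44 subjects and 352 subject-weeks are a ceiling that assumes every planned dropout is an ET, attends all further follow-up and loses the full 8 weeks. The actual figure depends on ET numbers, ET timing and willingness to return, none of which the documents give. The effect is on descriptive safety tables and possibly flare counts. It is worth correcting because the remedy is small and the lost events could not be recovered at analysis.

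**What to change.** Either delete the words about ET from the last part of footnote 15, or reword it so that:

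- for ET subjects, all AEs, AESIs and SAEs are collected regardless of causality through the post-treatment follow-up that Section 7.1.7 already sets, or to last contact if earlier;
- the related-SAE-only rule applies after that point, in line with Section 11.1.6;
- ET in this footnote means termination from the study.

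Make Sections 7.1.7, 11.1.4 and 11.1.6 agree on that single window. If data collection is already complete, the study report should state, by arm, which AEs were captured after ET.

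The cost is a wording change and AE data entry for the post-ET visits. No visits are added. Table 1 has no column for those visits and the case report form is not among the documents, so whether pages for them already exist needs checking.

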
Safety Outcome Measures:
	
Adverse events (AEs), AEs of special interest (AE-SI), clinical laboratory evaluations, vital signs, physical examinations including injection site evaluation and concomitant medication/treatment review.
 
Ophthalmic complications are well known to complicated severe AD with incidence rates of 32-56% (2, 3, 4, 5, 6, 7). Nonetheless, conjunctivitis has been a subject of interest in the dupilumab experience. Due to this experience, conjunctivitis and other ophthalmic events should be evaluated by an ophthalmologist and appropriate treatment rendered until resolution.

Mandatory Early Termination from Study Treatment
	
Using CTCAE Version 5.0 (Common Terminology Criteria for Adverse Events; https://ctep.cancer.gov/protocoldevelopment/electronic_applications/docs/CTCAE_v5_Quick_Reference_5x7.pdf), subjects who develop any related grade 2 or higher cardiovascular or respiratory treatment-emergent adverse events

	
(TEAE) or any related grade 3 or higher TEAE involving other organ systems must be discontinued from further study treatment dosing and monitored until resolution or stabilization.

Concomitant Medications:
	
The following treatments are not permitted, and any use must result in study treatment discontinuation if started after receiving the first dose of study treatment on D1:
 
 • Dupilumab or any antibody against IL-4Rα or IL-13 • Topical agents such as phosphodiesterase (PDE) inhibitors, Janus kinase (JAK) inhibitors, tacrolimus or pimecrolimus • Systemic treatment with steroids or other immunosuppressive and/or immunomodulating substances, e.g., cyclosporine, mycophenolate-mofetil, azathioprine, methotrexate or oral Janus kinase (JAK) inhibitors • Cell depleting agents, e.g. rituximab or treatment with other biologic therapeutics • TCM or Herbal medications for AD treatment including topical preparations 
Use of the following is also prohibited during the study participation:
 
 • Allergen immunotherapy • Live (attenuated vaccine) • Phototherapy (narrow band ultraviolet B [NBUVB], ultraviolet B [UVB], ultraviolet A1 [UVA1], psoralen + ultraviolet A [PUVA]), tanning beds, or any other light emitting device (LED) • More than 2 bleach baths per week

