11.1.1. AE Causality

The investigator’s assessment of causality must be provided for all AEs (serious and non-serious); the investigator must record the causal relationship on the CRF, and report such an assessment in accordance with the SAE reporting requirements, if applicable. An investigator’s causality assessment is the determination of whether there exists a reasonable possibility that the investigational product caused or contributed to an AE; generally, the facts (evidence) or arguments to suggest a causal relationship should be provided. The relationship of each AE to study medication will be assessed using the following categories:

Causality Category	Description
Related	An AE that follows a reasonable temporal sequence from administration of a drug (including the course after withdrawal of the drug), or for which possible involvement of the drug cannot be ruled out, although factors other than the drug, such as underlying diseases, complications, concomitant drugs and concurrent treatments, may also be responsible.
Not related	An AE that does not follow a reasonable temporal sequence from administration of a drug and/or that can reasonably be explained by other factors, such as underlying diseases, complications, concomitant drugs and concurrent treatments.

If the investigator does not know whether or not the investigational product caused the event, then the event will be handled as “related to investigational product” for reporting purposes, as defined by the sponsor. If the investigator cannot determine the etiology of the event but

determines that investigational product did not cause the event, this should be clearly documented on the case report form and SAE Report Form if applicable.

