11.2. Mandatory Early Termination

Using CTCAE Version 5.0, subjects who develop any possibly related grade 2 or higher cardiovascular or respiratory TEAE or any possibly related grade 3 or higher TEAE involving other organ systems must be discontinued from further study treatment dosing and monitored until resolution or stabilization.

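### The mandatory dosing stop depends on causality in the synopsis and Section 11.2 but not in Table 1 footnote 16, so it is unclear whether a qualifying-grade event judged not related ends treatment

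*Protocol*

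**What the plan says.** The rule appears in three places in the protocol, all in current text. In each, the consequence is mandatory: no more dosing, and follow-up until the event resolves or stabilises.

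- **Synopsis, Mandatory Early Termination from Study Treatment:** it covers "subjects who develop any related grade 2 or higher cardiovascular or respiratory treatment-emergent adverse events", and related events of grade 3 or higher in other organ systems.
- **Section 11.2:** it covers "subjects who develop any possibly related grade 2 or higher cardiovascular or respiratory TEAE", with the same qualifier on the grade 3 limb.
- **Table 1, footnote 16:** it covers "subjects who develop any CTCAE grade 2 or higher cardiovascular or respiratory TEAE or any grade 3 or higher TEAE involving other organ systems". Neither limb has a causality condition.

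Sections 11.1.1 and 11.1.4 allow two causality categories, related and not related. Related includes an event "for which possible involvement of the drug cannot be ruled out". Not related includes an event that "can reasonably be explained by other factors, such as underlying diseases".

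Section 7.1.2.3 treats AD flares as adverse events. When one occurs, "its onset and duration will be documented as an AE by the location(s) of flare involvement". Where the investigator gives permitted topical steroid as rescue, the section adds: "The subject need not be discontinued in this situation". The synopsis repeats this flare text.

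**The concern.** A mandatory safety rule needs one trigger that every site reads the same way. Here a site reading footnote 16 and a site reading Section 11.2 would reach different answers for the same subject if the event has a qualifying grade and is judged not related. About 60 sites are planned.

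Four things depend on which page is followed:

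- whether the subject is dosed again;
- whether that dose is a protocol deviation;
- whether the event enters the SAP Section 9.B count of TEAEs that led to stopping study drug;
- whether the subject may be left out of the Per Protocol Set for too little exposure (SAP Section 5.I).

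**Working it through.** There is no figure in the plan to reproduce. The check sets the three statements side by side and asks what each requires for each recordable causality category.

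**Step 1: the conditions.**

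| Place | Cardiovascular or respiratory | Other organ systems | Causality condition |
|---|---|---|---|
| Synopsis | Grade 2 or higher | Grade 3 or higher | Related |
| Section 11.2 | Grade 2 or higher | Grade 3 or higher | Possibly related |
| Table 1 footnote 16 | Grade 2 or higher | Grade 3 or higher | None |

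**Step 2: map the causality terms to the scale.** Possibly related is not a recordable category. The definition of related already takes in events where the drug's involvement cannot be excluded, so the synopsis and Section 11.2 select the same events in practice. Three wordings reduce to two outcomes.

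**Step 3: outcome for a qualifying-grade TEAE.**

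| Investigator's judgement | Synopsis | Section 11.2 | Footnote 16 | Mandatory stop |
|---|---|---|---|---|
| Related | Stop | Stop | Stop | 3 of 3 |
| Not related | Not required | Not required | Stop | 1 of 3 |

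**Step 4: look for text that settles it.** No passage gives one statement precedence. Section 8.3 leaves discontinuation from the study to the discretion of the investigator or sponsor, but does not set the minimum trigger of a mandatory dosing rule. Section 11.1.1 handles unknown causality as related for reporting, which does not reach events judged not related.

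**Step 5: an example.** Take an AD flare of grade 3, treated only with permitted topical steroid and judged not related because the underlying disease explains it. The flare is an AE. Section 7.1.2.3 says the subject need not be discontinued, footnote 16 says dosing must stop, and the synopsis rule and Section 11.2 do not apply.

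**Step 6: can the size be derived?** No rate of not-related TEAEs at these grades is given. The nearest information is in Section 5.4.2, where exacerbation of AD was the most common adverse event in the earlier AD study:

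- CBP-201: 0.261 × 23 = 6.0, so 6 subjects;
- placebo: 0.375 × 8 = 3.0, so 3 subjects.

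These counts cover any grade, and the same section says most TEAEs were mild. They show that flares are common, not how many would reach grade 3.

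**The case against.** The strongest reply is that no site faces incompatible orders. The synopsis and Section 11.2 say when dosing must stop; neither says it must continue after a not-related event. Stopping breaches none of the three statements, and continuing breaches only footnote 16. That is correct as logic, but it does not tell a site what the minimum trigger is or whether a further dose is a deviation.

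Placement is a second argument. Section 11.2 and the synopsis row are titled for this rule, while footnote 16 carries it as a closing note on unscheduled and early termination visits. This makes the titled statements easier to find, but it gives them no precedence. Footnote 16 is attached to the columns a site would consult when handling such an event.

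The objections to the flare example partly stand. Section 7.1.2.3 is permissive and can be read as saying only that topical steroid use is not in itself a reason to discontinue. Section 11.1.2 sets a demanding standard for grade 3. A flare that moves on to systemic rescue already ends dosing under Sections 7.1.2.3 and 8.4, whatever its causality. The remaining case, a grade 3 flare treated only with permitted topical steroid, may be uncommon. The contradiction does not depend on it.

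The analysis consequences are also modest. The discontinuation count is descriptive, Per Protocol exclusion is optional and decided in blind review, and the statistical conclusion rests on the Full Analysis Set. The wording in Section 11.2 looks like a remnant, since the summary of changes says the intermediate causality terms were dropped. It still needs correcting.

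**Conclusion.** The contradiction is real and must be fixed. It is confined to TEAEs of qualifying grade judged not related: footnote 16 mandates a stop and the other two statements do not. The number of such events cannot be derived from the documents.

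The rating rests on this being a mandatory safety rule with an indeterminate trigger, not on a numerical effect on the trial's conclusions. Section 11.1.4 keeps subjects under observation after treatment stops, so no loss of Week 16 data follows from the rule itself. The conclusion assumes only that investigators will use the two causality categories as Section 11.1.1 defines them.

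**What to change.** Reconcile the synopsis row, Table 1 footnote 16 and Section 11.2 with each other, with the causality categories in Sections 11.1.1 and 11.1.4, and with the flare text in Section 7.1.2.3 and the synopsis. State one trigger in identical words in all three places, using only the causality terms that can be recorded. Say explicitly how the rule applies to an AD flare recorded as an adverse event. Which version applies is for the sponsor to decide; this review takes no position on it.

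The cost is a protocol wording correction and a memo to sites, with no added procedures.
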